There is an internationally accepted protocol for the diagnosis of HT (Report of the Joint National Committee on Prevention, Detection, Evaluation and Treatment of High Blood Pressure, JNC 7 Report 2003⁽⁵⁾). Despite the protocol itself being well established, a new guideline for the definition of Stage I hypertension was published in 2017 by the American College of Cardiology/American Heart Association (ACC/AHA).⁽⁶⁾ The New Zealand Guidelines (2018) have been updated to comply with the new definition.⁽³⁾

Stage 1 hypertension is now defined as 130 to 139 mm Hg systolic or 80 to 89 mm Hg diastolic, and Stage 2 hypertension as 140/90 mm Hg or higher,⁽⁶⁾ thus bringing the 'prehypertension' group into the hypertension classification. Importantly management is centered around an assessment and treatment approach based on the cardiovascular risk rather than treating blood pressure as an isolated risk factor.^(3, 6, 7) For Stage 1 HT, management focusses on lifestyle factors in particular, physical activity, diet and reducing stress, rather than pharmacological interventions.^(3, 6-8)

Resistant hypertension (RHT) is a subset of HT. RHT is defined as 'blood pressure above the minimum level for hypertension despite concurrent use of three anti-hypertensive agents of different classes at optimal dose amounts, one of these being a diuretic'.⁽⁹⁾ Use of four medications including a diuretic is also considered as 'resistant' regardless of blood pressure values.⁽⁹⁾ An accurate account of compliance with medication and recorded blood pressure (BP) is important in the diagnosis of RHT to differentiate it from other categories of hypertension such as pseudo-hypertension, white coat hypertension and masked hypertension.⁽⁹⁾ Twenty four hour ambulatory blood pressure monitoring (24h APMB) has been shown to be the most effective and valid tool for diagnosing true RHT (TRHT).⁽⁶⁾ However, a key limitation of many studies that have investigated the management of RHT by focusing on lifestyle changes, such as an increase physical activity, have failed to diagnose TRHT within their cohorts.⁽¹⁰⁻¹²⁾

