Obstructive sleep apnoea (OSA) in adults has been correlated with the degree of blood pressure elevation above normal and thereby with the increasing risk of hypertension (HT).⁽¹³⁾ Thus, it is internationally accepted that OSA should be considered as a cause of both primary HT and secondary HT.^(1, 6, 7) The evidence has shown that OSA is linked with uncontrolled high blood pressure, more precisely, OSA has a close and strong relationship with RHT⁽¹⁾ and is cited as the most common secondary cause.⁽¹⁴⁾ Further, limited studies indicate, OSA has been associated with cardiac structure and function.⁽¹⁵⁾ However, relatively few studies have identified an association between OSA and TRHT.

It follows that since the severity of OSA is associated with major modifiable risk factors such as obesity and hyperaldosteronism in patients with RHT,⁽¹⁶⁾ reducing OSA through modifying the risk factor/s may be highly beneficial. Treatment for OSA is wide ranging and may include continuous positive airway pressure (CPAP).⁽¹⁷⁾ However, the goal of CPAP intervention is more to reduce symptoms rather than addressing the cause.⁽¹⁸⁾ Furthermore patient compliance is often low, due to the frustrations associated with the CPAP mask.⁽¹⁹⁾ Rather than just focusing on symptomatic management of OSA, it is suggested that new therapeutic strategies, that address OSA and HT simultaneously, may be more effective.⁽¹⁶⁾ In addition to CPAP management for OSA described above, increasing physical activity may be beneficial in treating both OSA⁽²⁰⁾ and BP⁽²¹⁾ as compliance with a prescribed physical activity programme can lead to a reduction in BP, and thereby, a reduction in the number of antihypertensive medications required by patients with HT.^(6, 7, 9, 22)

3. Aim of Study

To investigate the association between true resistant hypertension and high risk of obstructive sleep apnoea in a sub group of individuals diagnosed with resistant hypertension.

4. Objectives

To:

- determine the prevalence of true resistant hypertension (TRHT) measured by 24h ambulatory blood pressure monitoring in Dunedin based individuals with resistant hypertension (RHT);
- investigate the relationship between Epworth Sleepiness Scale scores and sleep fragmentation in the Dunedin based individuals identified with true resistant hypertension (TRHT);
- investigate the association between true resistant hypertension (TRHT) and high risk of obstructive sleep apnoea (OSA), in the Dunedin based individuals

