5. Hypothesis

5a. Primary Hypothesis

H_A: In Dunedin based individuals aged 60 years and below, diagnosed with resistant hypertension, 24h ambulatory blood pressure monitoring will identify a subgroup with true resistant hypertension.

H₀: In Dunedin based individuals aged 60 years and below, diagnosed with resistant hypertension, 24h ambulatory blood pressure monitoring will not identify a subgroup with true resistant hypertension.

5b. Secondary Hypotheses

H_A: There is correlation between Epworth Sleepiness Scale (ESS) score, and levels of sleep fragmentation in the subgroup of individuals with true resistant hypertension

H₀: There is no correlation between Epworth Sleepiness Scale (ESS) score, and levels of sleep fragmentation in the subgroup of individuals with true resistant hypertension

H_A: There is an association between true resistant hypertension and high risk of OSA, in the subgroup of individuals.

H₀: There is no association between true resistant hypertension and high risk of OSA, in the subgroup of individuals.

6. Study Design

The study is a descriptive observational study. The design has been selected to identify those with true resistant hypertension (TRHT) in a population of Dunedin based adults with resistant hypertension (RHT) and to investigate the risk of obstructive sleep apnoea (OSA) in the subset identified with TRHT. The anthropometric characteristics (body mass index (BMI), neck circumference, waist to hip ratio), cardio respiratory fitness (6MWT); quality of life (SF-36); and echo cardiogram parameters of the sub population with TRHT and high risk of OSA, will be determined to describe the study population.

7. Study Setting/ Location

The study is categorised as a single centre study at the University of Otago. The location will be the School of Physiotherapy, University of Otago ([name]). Specific investigations, and interpretation of data downloaded from 24hABPM and Echo-cardiography recordings, will be carried out in the Dunedin School of Medicine Cardiology Research Laboratory, on 9th floor of the Dunedin Public Hospital.

8. Study Population

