The PI will obtain the participant's demographic data (age; gender; ethnicity); general health and habits, physical activity level (initial assessment form – Appendix 1), quality of life (SF-36: Appendix 2) and OSA risk (ESS: Appendix 3), using self-administered questionnaires. Participants will use a tablet computer to complete this section which will take approximately 20 minutes. Data will then be downloaded onto the study data base (MS Excel).

The PI will then take the participant's resting blood pressure (office blood pressure – (BP)), heart rate, and peripheral saturation using standardised, calibrated equipment (NT1A Pulse oximeter, New Tech, Hamburg, Germany and Omron automatic digital blood pressure monitor, HEM 7322, Netherlands) and in accordance with the

ACC/AHA 2017 guidelines.⁽⁶⁾ Next, the PI will take the anthropometric (body weight, height and circumferences of neck, waist, hip,) measurements of the participant using standard guidelines⁽²⁵⁾ and equipment; electronic weighing scale (kg) and stadiometer (cm), measuring tape (scale in cm); with two decimal point accuracy. The equipment will be calibrated as required. This section of the procedure will take about 15 minutes. The variables, body mass index (BMI) and waist to hip ratio will be calculated using simple formulas on MS Excel.

The subset with RHT who also score ≥ 9 on the Epworth Sleepiness Scale (ESS) will be identified as 'at risk for OSA', and will be fitted with 24h ambulatory blood pressure monitor on the non-dominant upper arm, at the Cardiology Research Laboratory, on 9th floor in Dunedin Hospital. The participant will be advised to undertake daily activities/sleep as usual over the next 24 hours.

Appointment 2:

On the following day the device will be removed at the same setting, the Cardiology Research Laboratory, and data downloaded to confirm TRHT or not. Where TRHT is confirmed the participant will have an echo cardiogram to confirm baseline left ventricular function (results to be interpreted by co-investigator cardiologist).

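### TRHT is classified from the 24h ABPM alone, so three-drug participants with office pressure below the hypertension level but raised ambulatory pressure (masked hypertension) count as TRHT, although Section 2 lists masked hypertension as a separate category

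*Protocol*

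**What the plan says.** - **Definition (Section 2).** Three-drug RHT is "blood pressure above the minimum level for hypertension despite concurrent use of three anti-hypertensive agents of different classes at optimal dose amounts", one agent being a diuretic. The setting of the reading, office or ambulatory, is not given. Use of four drugs including a diuretic counts as resistant whatever the pressure.
- **Differentiation (Section 2).** An accurate account of compliance and of recorded blood pressure "is important in the diagnosis of RHT to differentiate it from other categories of hypertension such as pseudo-hypertension, white coat hypertension and masked hypertension".
- **Eligibility (Section 9).** A hypertension diagnosis and at least three prescribed antihypertensives including a diuretic. The list has no blood pressure condition. Section 11a says instead that participants meet the RHT definition, citing the same source as Section 2.
- **Appointment 1 (Section 11c).** The principal investigator takes the "resting blood pressure (office blood pressure" reading. Participants with RHT and ESS ≥ 9 are then fitted with the 24h monitor.
- **Appointment 2 (Section 11c).** The monitor is removed "and data downloaded to confirm TRHT or not".
- **Objective and hypothesis (Sections 4 and 5a).** The first objective is to "determine the prevalence of true resistant hypertension (TRHT) measured by 24h ambulatory blood pressure monitoring". The primary hypothesis is that "24h ambulatory blood pressure monitoring will identify a subgroup with true resistant hypertension".
- **Analysis (Section 12b).** Blood pressure is summarised, compared with guidelines and related to TRHT by regression, without saying whether office or ambulatory pressure is meant.

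**The concern.** In their ordinary meaning, white coat and masked hypertension are the two ways in which office and ambulatory pressure can disagree. An ambulatory reading keeps white coat cases out of TRHT, because their 24h pressure is not raised. It cannot identify masked cases, because their 24h pressure is raised just as in sustained resistance. Only the office reading separates the two. The study takes that reading and then gives it no part in the classification.

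Prevalence of TRHT is part of the primary outcome (Section 10), and Section 14 rests the study's novelty on isolating true resistance. If the numerator mixes sustained and masked cases in unknown proportion, the prevalence does not mean what Section 2 leads a reader to expect. The question cannot simply wait for the analysis stage: the label is applied at Appointment 2 and decides who has the echocardiogram, walk test and activity monitoring. Together with high OSA risk, it also decides who is invited to the second study.

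**Working it through.** **1. The plan's own figure.** Section 12a gives n = 83 for a population of 559, 95% confidence and a 10% margin. With p = 0.5 (my assumption; not stated):

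- n0 = 1.96² × 0.5 × 0.5 / 0.10² = 96.04
- n = 96.04 / (1 + 95.04/559) = 82.08, rounded up to 83

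The figure reproduces. It counts people in the sample, whereas ABPM goes only to those with ESS ≥ 9, a number the protocol does not give. The classification point does not depend on it.

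**2. What the rule does with each combination.**

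| Office BP | 24h ABPM | Label under Section 11c | Category |
|---|---|---|---|
| raised | raised | TRHT | sustained |
| raised | not raised | not TRHT | white coat |
| not raised | raised | TRHT | masked |
| not raised | not raised | not TRHT | controlled |

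Rows one and three receive the same label. Section 2 lists the category in row three as one to differentiate from RHT.

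**3. Who is affected.** On four or more drugs, Section 2 makes pressure irrelevant to resistance, so a normal office reading does not remove anyone. The problem is confined to participants on exactly three drugs. They can reach ABPM with office pressure below the hypertension level because the Section 9 list and the ESS cut-off set no pressure condition.

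**4. Size, by illustration only.** Among participants on exactly three drugs who receive ABPM, let c be the share with raised office pressure, s the share of those with raised ABPM, and m the share of the remainder with raised ABPM.

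- TRHT by ABPM alone = c·s + (1 − c)·m
- TRHT with masked cases removed from the numerator only = c·s
- Difference = (1 − c)·m

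All three inputs are assumptions: s = 0.6, m from 0.1 to 0.4, c as shown.

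| c | ABPM alone | Masked removed | Difference (points) | Masked share of numerator |
|---|---|---|---|---|
| 0.3 | 25–46% | 18% | 7–28 | 28–61% |
| 0.5 | 35–50% | 30% | 5–20 | 14–40% |
| 0.7 | 45–54% | 42% | 3–12 | 7–22% |

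Example: c = 0.3, m = 0.4 gives 0.3 × 0.6 + 0.7 × 0.4 = 0.18 + 0.28 = 0.46, and 0.28/0.46 = 61%.

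For all ABPM participants, multiply the difference by the share on exactly three drugs, which the documents do not give. The differences above are therefore ceilings for the whole ABPM group under each set of assumptions.

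**5. The denominator matters.** If raised office pressure were a condition of three-drug RHT, participants without it would leave the denominator as well. The three-drug prevalence would then be c·s / c = s = 60%, above every ABPM-alone value in the table. The TRHT count falls under either treatment; the direction of change in the proportion depends on how the definition is settled.

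**The case against.** The strongest reply is that the protocol has chosen its case definition and keeps to it. Sections 4, 5a, 11c and 14 all define TRHT by ABPM, and Section 2 says that ABPM "has been shown to be the most effective and valid tool for diagnosing true RHT (TRHT"). The sentence on differentiation is background text, concerns RHT rather than TRHT, and calls the matter important, not mandatory. The three-drug definition does not require an office reading, so someone on three drugs with raised 24h pressure arguably meets its words. Section 11a requires participants to meet the RHT definition, and Section 11c speaks of the subset with RHT after office pressure has been taken, so an office condition may be intended before ABPM.

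Much of this stands. An ABPM-defined case is a defensible choice, and the protocol does not show that masked cases are false positives. A reader might infer that TRHT should be redefined as both pressures raised. The documents do not support that as a blanket rule, since it would remove four-drug participants whom Section 2 calls resistant regardless of pressure.

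What the reply does not answer is that Section 2 asks for a distinction the procedure cannot make without office pressure. If an office condition is intended through Section 11a, neither Section 9 nor the Appointment 1 steps state it.

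**Conclusion.** The point stands in a limited form. Office pressure is measured but not used to classify RHT or TRHT, so masked cases on exactly three drugs are counted as TRHT without being identified. The size cannot be derived from the documents. The 3 to 28 points above rest wholly on assumed rates, apply to three-drug participants with ESS ≥ 9, and treat masked cases as staying in the denominator.

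Three further inferences are not supported:

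- **That office pressure is never used.** Section 12b may include it in the summaries and the regression. It is only the classification that omits it.
- **That a head count out of 83, or a bias matching the 10-point margin, can be stated.** Only those with ESS ≥ 9 receive ABPM, and any match with the margin would come from the chosen inputs.
- **That placing white coat cases with controlled ones blurs the comparison for OSA risk.** Everyone with ABPM already has ESS ≥ 9, and Section 11c identifies high OSA risk within the TRHT subset. Keeping white coat cases out of TRHT is also what ABPM confirmation is meant to do.

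**What to change.** 1. Reconcile Sections 2, 9, 11a and 11c on whether raised office pressure is a condition of RHT for participants on exactly three drugs. State the TRHT case definition in one place, covering office pressure, ABPM and drug count. This choice is the sponsor's.
2. Cross-classify every ABPM participant by Appointment 1 office pressure and ABPM (both raised, office only, ambulatory only, neither), separately for three-drug and four-or-more-drug users. The table needs a written cut-off for each pressure; Section 2 gives hypertension levels without saying how they apply to ambulatory readings. Confirm that each participant's drug count is recorded.
3. Report TRHT prevalence by ABPM alone and with three-drug masked cases excluded, give the denominator for each, and name in advance which is primary.

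The cost is a wording change and one extra table. Both pressures are already collected from everyone who receives ABPM, so no new visit or device is needed. The downsides are a possibly smaller TRHT count and small cells once the ABPM group is split by drug count.

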An initial appointment will then be arranged with each consenting adult. They will complete standardised health, OSA risk and activity questionnaires and have anthropometric measurements taken. The subset with RHT who also score ≥ 9 on the Epworth Sleepiness Scale (ESS) will be identified as 'at risk for OSA' and, will have, 24h ambulatory blood pressure monitoring (24hABPM) to confirm TRHT. For the subset with TRHT on the second appointment cardiorespiratory fitness will be measured using a six minute walk test (6MWT), and an echocardiogram will be completed. Sleep and physical activity monitoring for seven (24h) days/nights will then be undertaken using a wrist monitor to confirm sleep fragmentation. The outcome will be correlated with the ESS score to determine those at high risk of OSA.

As investigators will adhere to the new (2017) guideline for hypertension and include only those participants with TRHT, this will create a new knowledge dimension. The association between high risk of OSA and TRHT will be a key outcome measure. The outcomes from the echocardiogram, anthropometrics, activity parameters, and quality of life questionnaires will describe the population. The findings have potential to change the direction of research in the area, including opening the topic of TRHT to more debate and supporting modified guidelines for physicians and physiotherapists in managing the subpopulation with OSA and TRHT.

2. Background

Hypertension (HT) is a worldwide problem which affects at least one third of the adult population, numbering billions of people in the world.⁽¹⁾ Key determinants of the increasing prevalence of HT are increase in life expectancy, counterbalanced by factors such as an increase in both physical inactivity and obesity.⁽²⁾ Cardiovascular disease is the greatest cause of morbidity and mortality in New Zealand and the prevalence of HT in the adult population is over 30%, with ethnic disparities.^(3, 4) The Maori population is at a higher risk for HT compared to the other populations in New Zealand and has a higher use of antihypertensive medication - over 15% more than the New Zealand Europeans.⁽⁴⁾

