The population will comprise adults with resistant hypertension (RHT), based in the Dunedin region, aged 60 years and younger, who have been diagnosed with high blood pressure and are on three or more pharmacological agents of different classes including a diuretic. The population has been drawn from the Ministry of Health Pharmaceutical Collection Warehouse, via the Best Practice Advocacy Centre (bpac),⁽²³⁾ New Zealand.

The total number of adults with hypertension and being pharmacologically managed with three or more antihypertensive medications (estimated RHT) in New Zealand is 100,340; Southern District Health Board, 8425; and in the Dunedin region, 3184. The number of adults 60 years age or below in the Dunedin region with RHT is 559.⁽²⁴⁾

9. Eligibility Criteria

Inclusion criteria

- Age: 18-60 years inclusive
- Gender: all
- Able to communicate/follow instructions in English
- Based in Dunedin region
- Diagnosed with hypertension
- Prescribed three or more antihypertensive medications including a diuretic (RHT definition⁽⁹⁾).

Exclusion criteria

- Diagnosed with hypertension prescribed two or less antihypertensive medications
- Adults above the age of 60 years
- Diagnosed/known renal disease
- Females who are pregnant

10. Study Outcomes

Primary Outcome

The prevalence of TRHT in a population with RHT and the association of TRHT with high risk of OSA.

Secondary Outcome(s)

The correlation between increased Epworth Sleepiness Scale score and sleep fragmentation in the subset with true resistant hypertension.

11. Study Procedures

a. Recruitment of participants

Adults (18-60y) in the Dunedin region, [anonymized] on three or more pharmacological agents of different classes, and the general practices [anonymized] they are enrolled at, have been identified from the Ministry of Health Pharmaceutical Collection Warehouse, via the Best Practice Advocacy Centre (bpac),⁽²³⁾ New Zealand. The number of adults on the list is 559⁽²⁴⁾, [the list of names will remain de-identified to the research team as letters will be forwarded by General Practitioners].

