Socio demographic data/ health status and habits/ adherence to medications	Self-administered questionnaire (Appendix I)
Office blood pressure	Digital BP monitor (Omron automatic digital blood pressure monitor, HEM 7322, Netherlands)
Heart rate and peripheral oxygen saturation	NT1A Pulse oximeter, New Tech, Hamburg, Germany
Height	Stadiometer ⁽²³⁾
Weight	Electronic weighing scale ⁽²³⁾
Neck, hip, waist circumference	Measuring tape (cm) ⁽²³⁾
Risk of OSA	ESS scale ^(27, 28) (Appendix II)
Quality of life	SF-36 (Appendix III)
Exercise readiness	PARQ+ 2017 (appendix IV)
Cardiorespiratory fitness	6MWT (Appendix V)/ Borg Rating of Perceived Exertion Scale ⁽¹⁰⁾
24h ABPM	ABPM (90207, Spacelabs, Snoqualmie, Washington, USA ⁽¹⁰⁾)
Functional activity [step count, time in low/moderate/vigorous physical activity, sedentary time]	ActiGraph GT3XPB, Pensacola, Florida ⁽²⁶⁾ .
Objective sleep measurements [total sleep time, awakenings, average awakenings, sleep efficiency, sleep onset, latency and wake after sleep onset]	ActiGraph GT3XPB, Pensacola, Florida ⁽²⁶⁾ .
Echocardiography [Interventricular septal end diastole and end systole (IVSd and IVSs), Left ventricular internal diameter end diastole and end systole (LVIDd and LVIDs), Left ventricular posterior wall end diastole and end systole (LVPWd and LVPWs), Left ventricular ejection fraction (LVEF%), Right ventricular end diastole (RVDd), Aortic root diameter (Ao Root Diam), Left atrium diameter (LA Diam), Mitral and Aortic valve regurgitations (MR and AR)]	Cardiac ultrasound machine

11e. Safety considerations/Patient safety

This study can be categorised as a minimal risk observational study, based on the guidelines of Health and Disability Ethics Committees (HDEC). No invasive clinical or non-clinical procedures or equipment are involved in the proposed study. Activity involving equipment available in a gymnasium setting will be applied, (Table 1). Only the calibrated equipment and standardised tests outlined above will be used in the study.

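### True resistant hypertension is classified from 24h ABPM alone, so participants with raised ABPM who do not take their drugs are counted as truly resistant, although adherence is collected

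*Protocol*

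**What the plan says.** Wherever the Protocol describes how TRHT is determined, the determinant is ABPM:

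- Introduction: "24h ambulatory blood pressure monitoring (24hABPM) to confirm TRHT".
- Section 4, first objective: "determine the prevalence of true resistant hypertension (TRHT) measured by 24h ambulatory blood pressure monitoring".
- Section 5a, primary hypothesis: "24h ambulatory blood pressure monitoring will identify a subgroup with true resistant hypertension".
- Section 11c, Appointment 2: "data downloaded to confirm TRHT or not".

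Section 10 makes the prevalence of TRHT, and its association with high risk of OSA, the primary outcome.

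On drug use, section 2 defines resistant hypertension (RHT) as raised pressure despite "concurrent use of three anti-hypertensive agents of different classes at optimal dose amounts", and adds: "An accurate account of compliance with medication and recorded blood pressure (BP) is important in the diagnosis of RHT". Section 9 admits on prescription: "Prescribed three or more antihypertensive medications including a diuretic". Table 1 in section 11d lists, as a self-administered questionnaire item, "Socio demographic data/ health status and habits/ adherence to medications". The adherence answer is not mentioned in the TRHT rule in 11c or among the regression variables in 12b.

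**The concern.** ABPM measures pressure. It can separate a raised clinic reading from sustained hypertension, but it cannot show whether the prescribed drugs were taken. Entry rests on a dispensing-database list and a prescription criterion, and nothing stated between entry and the ABPM result checks use. Two different groups therefore end up in one category: people whose pressure stays high on treatment, and people whose pressure is high because treatment is not taken.

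This matters because the study's stated contribution is to separate true from apparent resistance. The mixing affects the numerator of the primary prevalence and the make-up of the group on which the later TRHT analyses are run. It is a bias in classification, so a larger sample would not reduce it.

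**Working it through.** **The Protocol's own figure.** Section 12a gives n = 83 for a population of 559, 95% confidence and a 10-point margin. With an expected proportion of 0.5 (not stated; assumed) and a finite-population correction:

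- n0 = 1.96² × 0.25 / 0.10² = 96.04
- n = 96.04 / (1 + 95.04/559) = 82.1, rounded up to 83.

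The figure reproduces. It concerns precision only and does not depend on how TRHT is defined.

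**The classification rule, step by step.**

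| Step | What is required | Does it check drug use? |
|---|---|---|
| Definition of RHT (section 2) | Concurrent use of three agents | Yes, in principle |
| Entry (section 9) | Three or more agents prescribed | No |
| Questionnaire (Table 1) | Adherence recorded | Recorded, but tied to no rule |
| TRHT status (11c) | ABPM download | No |
| Analysis (12b) | Adherence not listed | No |

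A non-adherent participant with raised ABPM passes every operative step and is classed as TRHT.

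**Size.** Let p be the proportion ABPM-positive among those monitored, q the non-adherent share of the positives, and r the share of those non-adherent positives who would still be uncontrolled if they took their drugs. With the denominator unchanged:

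- reported prevalence = p
- prevalence of resistance on treatment = p(1 − q) + p·q·r
- overstatement = p·q·(1 − r), which is at most p·q, reached when r = 0.

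The Protocol gives none of p, q or r. With p and q assumed, the upper bound p×q in percentage points is:

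| | q = 10% | q = 20% | q = 30% | q = 40% |
|---|---|---|---|---|
| p = 30% | 3 | 6 | 9 | 12 |
| p = 50% | 5 | 10 | 15 | 20 |
| p = 70% | 7 | 14 | 21 | 28 |

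For example, 0.30 × 0.10 = 0.03 and 0.70 × 0.40 = 0.28. Any r above zero lowers every cell in proportion.

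**The case against.** The best defence is that the Protocol's concept of TRHT is ABPM-based and consistently so. Section 2 ranks ABPM as the best tool for diagnosing TRHT, and section 14 treats it as the reference standard. The remark on compliance is attached to RHT, one step earlier, and the word used is important, not required. A reader might infer that the Protocol makes adherence a condition of TRHT and then breaks its own rule. The text does not go that far. What stands is narrower: TRHT is a subset of RHT, RHT is defined by use, and nowhere does the Protocol say that ABPM replaces the account of compliance.

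Adherence might also be meant to act upstream, since section 11a asks that participants meet the RHT definition and the questionnaire comes before ABPM. But section 9 equates that definition with prescription, so no such screen is stated. Appendix I and the flow diagram are not visible and no SAP is at hand. The absence of adherence from 12b is therefore weak evidence by itself, and the point rests on the case definition, which the Protocol fixes in its objective, hypothesis and procedure.

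Three further inferences are tempting and should not be drawn:

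- **That the points in the table are the expected bias.** They are ceilings on assumed inputs. Some non-adherent participants would stay uncontrolled on treatment, and the true number affected is unknown.
- **That the bias can be set against the planned ±10 points.** That margin belongs to n = 83 drawn from the RHT population. Section 11c fits ABPM only to those scoring 9 or more on the Epworth scale, so the prevalence denominator is smaller and its precision is not ±10.
- **That sleepiness, through poorer adherence, distorts the TRHT–OSA association.** The Protocol gives no figure for such a link, and everyone who receives ABPM has already been selected on the sleepiness score.

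**Conclusion.** The point holds in this form: the case definition of the primary outcome rests on ABPM alone in people selected on prescription, while the Protocol defines resistance by use, calls compliance important to the diagnosis, and collects adherence without saying how it is used. Followed as written, participants with raised ABPM who do not take their drugs are counted as truly resistant, and TRHT prevalence can be overstated by up to p×q. For assumed p of 30–70% and q of 10–40% that ceiling is 3 to 28 percentage points. The direction follows from the written rule; the size rests wholly on the assumed inputs. The required n of 83 is unaffected.

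**What to change.** Leave the ABPM procedure and participant flow as they are. TRHT status in 11c also decides who goes on to echocardiography, the walk test, actigraphy and the second-study invitation, so rewriting it there would change more than the analysis. Instead, state in sections 10 and 12b that the primary prevalence and the TRHT analyses are reported two ways, over the same denominator of participants with ABPM:

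- (a) all ABPM-positive participants, labelled 'ABPM-confirmed uncontrolled BP on three or more prescribed agents';
- (b) ABPM-positive participants who self-report adherence, labelled TRHT, with ABPM-positive non-adherent participants shown separately as apparent RHT.

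State before the data are examined which questionnaire answer counts as adherent.

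The cost is wording in two sections and an additional set of tabulations and analyses from data already collected, with no new visit or measurement and no change to n. The downsides are a smaller TRHT group in (b) and a partial correction: self-report overstates adherence, so some non-adherent participants will remain in (b), while (b) also drops any non-adherent participants who would have stayed uncontrolled on treatment. Showing both figures lets readers see how much the result depends on the definition.
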